## **8.2 Procedures for recording and reporting adverse events (AE)**

The investigator must record all AEs presented or reported by the patient in the AE section of the eCRF. The start date, the actions taken (concomitant treatments, discontinuation of treatment, dose change, premature withdrawal, none, other) and the outcome (ongoing, not recovered, recovered with / without sequelae, death, unknown) must all be recorded and the investigator must assess the event in terms of seriousness, severity and relationship to the conservative or invasive treatments studied.

When possible, signs and symptoms should be reported as a diagnosis i.e. the investigator should avoid reporting only the signs and symptoms. If there is no medical diagnosis and the signs and symptoms have to be reported, the investigator should record a separate AE for each sign and symptom.

The severity of the AEs will be judged by the investigator(s) and recorded as follows:

- Mild: discomfort noticed but no disruption of normal daily activity,
- Moderate: discomfort sufficient to reduce or affect daily activity,
- Severe: inability to work or perform normal daily activity.

The relationship of the AE to the conservative or invasive treatments will be judged by the investigator(s) and recorded as follows:

- Related: there is reasonable causal relationship between the treatment and the AE,
- Unrelated: there is no reasonable causal relationship between the treatment and the AE.

The proposed study is observational research that makes use of data collected as part of routine care and does not involve alteration of clinical care. Investigators should follow usual reporting rules to fulfil Belgian pharmacovigilance reporting.

Safety evaluations for this study are limited to the specified safety outcomes stated in [Section 8.1](#).

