#### **4.4.2 Study setting**

The GP examines the patient and makes the diagnosis of CVD, based on clinical signs and symptoms. Patients who receive a diagnosis of CVD according to international guidelines who require conservative or invasive treatment can be included in the study. Duplex ultrasound or any other specific examination is not required to make the diagnosis, but could be done if needed according to routine clinical practice and recommendations. Each participating GP (120 GPs) will select approximately between 10 and 15 patients with CVD.

During the inclusion visit (V0), a treatment strategy will be proposed to the patient with confirmed CVD by the GP. The treatment can be conservative or invasive, depending on the severity of the disease. Patients awaiting invasive treatment may receive conservative treatment to alleviate symptoms. The choice of treatment modality is left to the discretion of the treating physician, in agreement with the patient and according to local policies. As this is an observational study, there will be no interference in the choice of treatment, and no restrictions will be imposed.

Commonly proposed conservative treatment options include compression therapy, and oral or topical venoactive drugs. If the GP decides that the patient needs an invasive treatment, then the patient will be referred to a venous centre. The specialist to whom the patient is referred, chooses the type of invasive treatment, as done in standard clinical care. The specialist may also prescribe conservative treatment to the patient, either while awaiting invasive treatment or in case invasive treatment is not deemed necessary.

[figure not shown]
Patients and their GP may decide to switch at any time between conservative treatments or to undergo an intervention as secondary/add-on treatment to conservative treatment.

Baseline data will be collected by the GP on the day of the V0. Follow-up visits, which are expected to take place within the scope of routine clinical practice, will be organized by the GP at defined timepoints after the V0: at 6 weeks, 12 weeks, 6 months, 12 months and 24 months of follow-up (V1-V5).

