A delay between referral to the venous centre during the V0 and the day of invasive treatment is anticipated. To allow assessment of the primary study objective, GPs will be asked to invite the patients for a follow-up visit 12 weeks after the invasive treatment took place (V-i), provided that it falls within the scope of routine medical practice in terms of visit frequency.

Due to the real-world setting, patients might not be assessed exactly at the proposed weeks/months. Therefore, some visits may not take place if they are not within the scope of regular medical practice. Additionally, a time range around the visits will be allowed. The frequency of follow-up visits is upon the discretion of the treating physicians.

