## 8. Assessment of safety

### 8.1 Specification, timing and recording of safety parameters

According to the International Conference on Harmonisation (ICH), an **AE** is any untoward medical occurrence in a subject or clinical investigation subject administered a pharmaceutical product and which does not necessarily have a causal relationship with this treatment. An AE can therefore be any unfavourable and unintended sign (including an abnormal laboratory finding), symptom or disease temporally associated with the use of a medicinal (investigational) product, whether or not related to the medicinal (investigational) product. Worsening of a pre-existing condition during the study must also be recorded as an AE.

A Treatment Emergent Adverse Event (**TEAE**) is defined as any event not present prior to the initiation of the treatments or any event already present that worsens in either intensity or frequency following exposure to the treatments.

A Serious Adverse Event (**SAE**) is defined as any untoward medical occurrence that:

- Results in death,
- Is life-threatening (the term 'life-threatening' refers to an event in which the subject was at risk of death at the time of the event; it does not refer to an event which hypothetically might have caused death if it were more severe),
- Requires inpatient hospitalisation or prolongation of existing hospitalisation,
- Results in persistent or significant disability or incapacity,
- Is a congenital anomaly or birth defect.

Pharmacovigilance data include any unintended or adverse event associated with the use of a medicinal product in humans, whether or not considered drug related, including the following special situations (situations where no AE occurred but information needs to be collected):

- Exposure during pregnancy (maternal and/or transmission of a medicinal product via semen following paternal exposure) or breastfeeding,
- Overdose, abuse, misuse, off label use, medication error, occupational exposure,
- Drug-drug or drug-food interactions,
- Any suspected transmission via a medicinal product of an infectious agent,
- Unintended therapeutic benefit,
- Lack of efficacy.

AEs and special situations will be assessed during each follow-up visit and recorded in the eCRF.

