### **9.2 Sample size**

Considering a Minimum Clinically Important Difference (MCID) of 5 points before/after treatment for the primary endpoint (CIVIQ-20 GIS), a default correlation of 0.5, and with an expected drop-out of 60% of patients in the conservative group and 25% in the invasive group, we propose the recruitment of 1650 patients (safe margin), to finally include minimally 1590 patients (power 90%).

Each investigator (120 GPs) will recruit approximately between 10 and 15 consecutive patients.

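### Section 8.2 gives no route for AEs documented at the venous centre to reach the eCRF, so AEs after an intervention may be under-ascertained

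*Protocol*

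**What the plan says.** Section 8.2 (recording and reporting of AEs) states: "The investigator must record all AEs presented or reported by the patient in the AE section of the eCRF". Section 8.1 adds the timing: "AEs and special situations will be assessed during each follow-up visit and recorded in the eCRF". Table 1 schedules AEs at V1 to V5 and at V-i.

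The investigators are the GPs. Section 9.2 says: "Each investigator (120 GPs) will recruit approximately between 10 and 15 consecutive patients". Section 4.4.2 places invasive treatment elsewhere: "If the GP decides that the patient needs an invasive treatment, then the patient will be referred to a venous centre". It continues: "The specialist to whom the patient is referred, chooses the type of invasive treatment, as done in standard clinical care". The protocol does not name the centre as a study site, nor does it give the centre or the specialist any reporting duty.

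V-i is set 12 weeks after the intervention, if routine practice allows, and under Table 1 it replaces any visit that it overlaps. Section 4.4.2 also accepts that "some visits may not take place if they are not within the scope of regular medical practice".

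The GP nevertheless has to assess causality. Section 8.2 says: "The relationship of the AE to the conservative or invasive treatments will be judged by the investigator(s) and recorded as follows".

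Safety is secondary objective 9, and its endpoint counts patients with AEs. Section 9.3.3 analyses the secondary endpoints in the Analysis Set, overall and by treatment group.

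**The concern.** The only source of AEs that the recording rule names is the patient, seen by the GP. Conservative treatment is mostly managed by that same GP. A procedure is done at the centre, where an early complication may be seen, treated and resolved before the patient next sees the GP. If the patient does not mention it weeks or months later, nothing in the protocol brings it into the eCRF, even when a letter from the centre is in the GP's file. Practice may also differ between GPs, since some will consult such letters and others will not.

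At stake is the completeness of the AE proportion after an intervention. Events never collected cannot be recovered at analysis. Section 9.1 discusses selection, attrition and measurement bias, but it does not mention how AEs are ascertained.

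**Working it through.** The protocol states no AE rate and no reporting fraction, so there is no figure to reproduce. The check sets the provisions side by side and then illustrates the possible size.

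**Step 1: routes into the eCRF**

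- *From the patient to the GP:* stated in 8.2, at the visits named in 8.1.
- *From the centre to the GP to the eCRF:* not stated. The GP is not told to obtain, or to check for, a procedure or discharge report.
- *From the centre directly to the eCRF:* not stated.

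**Step 2: timing**

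V-i comes 12 weeks after the intervention and may not take place. Section 7 describes it for the invasive group. For an add-on intervention in the conservative group, the next opportunity may be a scheduled visit. The later scheduled visits are 12 - 6 = 6 months apart (V3 to V4) and 24 - 12 = 12 months apart (V4 to V5).

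**Step 3: size within patients who have an intervention (all inputs assumed)**

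Let p be the true proportion of patients with a procedure-related AE, and m the share of those patients whose event never reaches the eCRF. Then recorded proportion = p × (1 - m):

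| True p | m = 10% | m = 25% | m = 50% |
|---|---|---|---|
| 5% | 4.5% | 3.75% | 2.5% |
| 10% | 9.0% | 7.5% | 5.0% |
| 20% | 18% | 15% | 10% |

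The shortfall p × m runs from 0.5 points (0.05 × 0.10) to 10 points (0.20 × 0.50). This is an upper bound for the planned endpoint, which counts patients with any AE. If a share r of the affected patients have another recorded AE, the shortfall is p × m × (1 - r). The table is the case r = 0.

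**Step 4: does the gap fix a direction between groups?**

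Section 9.2 expects drop-out of 60% in the conservative group and 25% in the invasive group, so retention is 0.40 and 0.75. As a crude bound, suppose that the true risk is 10% in both groups, that AEs are seen only in retained patients, and that all enrolled patients form the denominator:

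- No loss at the centre: invasive 0.10 × 0.75 = 7.5%; conservative 0.10 × 0.40 = 4.0%.
- m = 25%: invasive 0.10 × 0.75 × 0.75 = 5.6%; conservative 4.0%.
- m = 50%: invasive 0.10 × 0.50 × 0.75 = 3.75%; conservative 4.0%.
- Break-even: m = 1 - 0.40/0.75 = 47%.

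On these assumptions the invasive group would look safer only if nearly half of its affected patients went unrecorded. The bound is crude because drop-outs contribute AEs until they leave, and because the Analysis Set requires at least one follow-up visit. It shows only that the sign cannot be read from the protocol.

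**The case against.** The strongest reply is that the sentence in 8.2 imposes a duty and does not limit sources. A reader might infer that GPs may record nothing except what patients report, but the text contains no such restriction. An AE that is presented can include what the GP observes. Section 8.1 defines AEs broadly and requires them to be assessed at every follow-up visit. Section 8.2 lists death as an outcome, which a patient cannot report. The study uses routine-care data, section 10.1 provides for source document verification, and section 11 counts patients' case sheets as source documents. The eCRF and the SAP are not shown and may contain prompts for procedural events. All of this stands, and it is why the events can be said only to be possibly missed. It does not close the gap, since none of these provisions directs the GP to the centre's reports.

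A reader might also infer that invasive treatment will look safer than conservative treatment. The documents do not support that. The invasive group has its own visit (though V-i may replace another) and a lower expected drop-out. Skipped visits affect both groups. Conservative patients with an add-on intervention carry the same gap inside the conservative group. No between-group safety test is planned; AEs are only described.

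Finally, checking the GP's file does not recover an event for which no report ever reaches the GP. That is correct, and the remedy therefore includes a stated limitation.

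**Conclusion.** The point holds as a possible under-ascertainment of procedure-related AEs after any intervention, initial or add-on. It rests on three features of the protocol: the recording rule names only the patient as source, the venous centre has no stated role in data collection, and the dedicated post-intervention visit is late and optional. The proportion of patients with AEs after an intervention may be understated. The size is unknown: the illustrative 0.5 to 10 points rest wholly on assumed risks and loss fractions and are upper bounds for an endpoint that counts any AE. The direction of any between-group difference is not established. This is a cheap improvement to data collection for secondary endpoint 9; it does not affect the primary endpoint.

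**What to change.** 1. In section 8.2, extend the recording sentence so that, after the reference to the patient, it continues: *or documented in the patient's medical file, including reports received from the venous centre*.
2. Have the GP check the file for such events at V-i, or at the first visit after any intervention, in either treatment group.
3. Add an eCRF item for the source of each AE (patient or venous-centre report).
4. In section 9.1, name the remaining under-ascertainment, that is, events for which no report reaches the GP, as a limitation.

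The cost is one sentence in 8.2, a short instruction for the file check, one eCRF item, a line in 9.1, and a few minutes of file review per patient with an intervention. No visit, procedure or treatment decision changes, so the study remains observational.

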### **8.3 Treatment stopping rules**

Discontinuation or withdrawal of treatment will be decided in accordance with regular medical practice and according to the physician's judgment.

## **9. Statistics**

### **9.1 Risk of bias**

The results obtained during this study may be biased through selection of the treating physicians and the willingness of patients to participate. To minimize the bias related to GP representativity, GPs will be selected throughout Belgium. The GPs will be asked to offer the study to all patients who meet the eligibility criteria, and to select consecutive patients whenever possible. GPs will receive a training before the start of the study.

The statistical model will adjust for the period during which the patients in the invasive treatment group had not yet received the intervention (i.e., the time between inclusion at V0 and the day of the intervention) (See [Section 9.3 Analysis](#)).

Patients lost to follow-up may cause attrition bias. To minimize this bias, efforts will be made to contact the patients if they are lost to follow-up.

To minimize the risk of measurement bias, each GP will receive a training on the use of the assessment instruments (CEAP, rVCSS, CIVIQ-20, VAS) before the site activation.

### **9.2 Sample size**

Considering a Minimum Clinically Important Difference (MCID) of 5 points before/after treatment for the primary endpoint (CIVIQ-20 GIS), a default correlation of 0.5, and with an expected drop-out of 60% of patients in the conservative group and 25% in the invasive group, we propose the recruitment of 1650 patients (safe margin), to finally include minimally 1590 patients (power 90%).

Each investigator (120 GPs) will recruit approximately between 10 and 15 consecutive patients.

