## 9.3 Analysis

### 9.3.1 Statistical hypotheses

All statistical tests will be two-sided at the 5% overall alpha risk level. All Confidence Intervals (CIs) will be two-sided and presented at the 95% confidence level. No alpha risk adjustment is planned.

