### **Primary endpoint**

The analyses will be conducted in the AS.

To evaluate the change in the CIVIQ-20 GIS from V0 to a visit realized 12 weeks after the beginning of the treatment (or day of the intervention for patients in the invasive group) in each treatment group, we will compare the V0 value with the value at 12 weeks with a paired t-test or Wilcoxon signed-rank test depending on the distribution of GIS of CIVIQ-20 in each treatment group.

A mixed model could be conducted, with the GIS of CIVIQ-20 as the dependent variable, the visit as a fixed effect and time between V0 and the day of the intervention as covariate and paired on the patient in the invasive group.

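### The stated 90% power for 1590 patients and the 5% overall alpha are not supported by a design that tests each treatment group separately, leaves the group split to usual care and samples patients through about 120 GPs

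*Protocol*

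**What the plan says.** Section 9.2 (repeated in the synopsis) starts from "Considering a Minimum Clinically Important Difference (MCID) of 5 points before/after treatment for the primary endpoint (CIVIQ-20 GIS"), adds a before/after correlation of 0.5 and expected drop-out of 60% (conservative) and 25% (invasive), and concludes "we propose the recruitment of 1650 patients (safe margin), to finally include minimally 1590 patients (power 90" per cent). It gives no SD, group split or allowance for clustering, and does not say whether the 90% refers to each group, to both together or to the pooled sample.

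On recruitment the same section says "Each investigator (120 GPs) will recruit approximately between 10 and 15 consecutive patients". Section 4.4.2 leaves the choice between conservative and invasive treatment to the treating physician and the patient.

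For the primary endpoint, section 9.3.3 says "we will compare the V0 value with the value at 12 weeks with a paired t-test or Wilcoxon signed-rank test", and applies this within each treatment group. An optional mixed model for the invasive group is paired on the patient; no GP term is named.

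Section 9.3.1 says "All statistical tests will be two-sided at the 5% overall alpha risk level" and, in the same paragraph, "No alpha risk adjustment is planned".

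**The concern.** Three stated or implied properties of the design do not follow from what is written.

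- **Power.** When the test is done within a group, power belongs to the group. A single total fixes it only if the split is known, and here the split is an outcome of routine care. With no per-group target, nobody would notice the smaller group falling short.
- **Alpha.** Two primary tests, each at 5% and unadjusted, do not have an overall level of 5% unless a decision rule makes them so. No such rule is given.
- **Independence.** The GP proposes the treatment and organises the follow-up visits, so changes in patients of the same GP may be correlated. The paired test treats all patients as independent. If that correlation is positive, the confidence intervals are too narrow, and in a mainly descriptive study the intervals are the principal result.

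**Working it through.** **Inputs from the protocol.** Difference 5 points; correlation 0.5, so the SD of the change equals the SD of one score if the two visits have equal SDs; two-sided 5%; power 90%; retention 0.40 (conservative) and 0.75 (invasive); total 1590; 120 GPs. **Not in the protocol, so assumed or solved for:** the SD, the split, and the intracluster correlation (ICC) of the change.

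**1. Trying to reproduce 1590.** For a paired mean, the evaluable number per group is n = (1.960 + 1.282)² × SD² / 5² = 10.507 × SD² / 25. Enrolment for two equal evaluable groups is n/0.40 + n/0.75. Without an SD this has no single answer, so I solved backwards:

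- n = 1590 / (1/0.40 + 1/0.75) = 1590 / 3.833 = 414.8 per group
- SD of change = 5 × √414.8 / 3.2415 = 31.4
- enrolled: 414.8/0.40 = 1037 conservative and 414.8/0.75 = 553 invasive, i.e. about 65:35

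The implied SD depends on the formula: a two-sample calculation would need 22.2. Hence 1590 can be matched but not derived from the stated inputs.

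**2. Power per group at a total of 1590.** Power = Φ(5√n / SD − 1.96), with n = 1590 × share × retention, patients taken as independent.

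| Split cons:inv | Evaluable cons / inv | SD 31.4: cons / inv | SD 20 (assumed): cons / inv |
|---|---|---|---|
| 50:50 | 318 / 596 | 81% / 97% | 99% / >99% |
| 65:35 | 415 / 415 | 90% / 90% | >99% / >99% |
| 80:20 | 509 / 238 | 95% / 69% | >99% / 97% |
| 90:10 | 572 / 119 | 97% / 41% | >99% / 78% |

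Example, invasive group at 80:20 and SD 31.4: 1590 × 0.20 × 0.75 = 238.5; 5 × √238.5 / 31.4 = 2.459; Φ(2.459 − 1.96) = 0.69.

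**3. Alpha.** The two groups contain different patients. If both null hypotheses are true and a positive result in either group counts, the familywise error is 1 − 0.95² = 9.75%.

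**4. Clustering.** In the back-solved case there are 415/120 = 3.46 evaluable patients per GP per group. Design effect DE = 1 + (3.46 − 1) × ICC; power = Φ(3.2415/√DE − 1.96); interval coverage = 2Φ(1.96/√DE) − 1.

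| ICC of change (assumed) | DE | Nominal 90% power becomes | 95% interval covers |
|---|---|---|---|
| 0.02 | 1.05 | 89% | 94.4% |
| 0.05 | 1.12 | 86% | 93.6% |
| 0.10 | 1.25 | 83% | 92.1% |

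**The case against.** **Power may be ample.** A reader might infer that the true power is below 90%. The protocol does not show this. At an assumed SD of 20, power is at least 97% in both groups at any tabulated split from 50:50 to 80:20. This objection stands: the figure cannot be verified, but no arithmetic error has been demonstrated.

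**1590 analysed?** A reader might take the 1590 as patients analysed and see a contradiction with drop-out, since 1650 recruited would leave only between 1650 × 0.40 = 660 and 1650 × 0.75 = 1237. That is not the natural reading. Section 9.2 speaks of including patients, and the Included Set in section 9.3.2 is defined by inclusion and signed consent. One clarifying phrase is enough.

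**Alpha.** The study is mainly descriptive, the absence of adjustment is openly declared, and 9.75% needs both nulls true with either success counting. If both groups had to be positive there would be no inflation. All of this is fair. What remains is that the word *overall* is untrue as written.

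**Clustering.** The ICC is not in the protocol. CIVIQ-20 is completed by the patient, stable GP effects on the score level cancel in a before/after change, and in the invasive group the specialist chooses the procedure, so the GP may not be the main cluster there. A larger loss is tempting but unsupported. It would need about 1590 × 0.40 / 120 = 5.3 evaluable patients per GP in one group, which means every patient is conservative. That group would then have 636 evaluable patients and, at SD 31.4, 98% power before clustering and still 92% at a design effect of 1 + 4.3 × 0.10 = 1.43.

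**Left to the SAP.** Model detail can be settled there, and section 9.3.3 mentions random intercepts without naming a level. But the protocol itself names the primary test, and that test assumes independence.

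**Conclusion.** The point holds in three parts of unequal strength.

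- **Power: firm that it is unsupported.** This rests on the protocol's text alone: tests by group, one total, no SD and no split. The size of any shortfall depends on the unknown SD and split, with invasive-group power from 97% down to 41% at SD 31.4 across splits of 50:50 to 90:10, and 97% and 78% at SD 20 for 80:20 and 90:10.
- **Alpha: firm as a contradiction in wording.** The worst case is 9.75%, under the conditions given above. The practical consequence is limited in a mainly descriptive study.
- **Clustering: a real omission of modest size.** At an assumed ICC of 0.02 to 0.10 and about 3.5 evaluable patients per GP per group, the design effect is 1.05 to 1.25. Whether the intervals really are too narrow depends on the ICC being positive, which the protocol cannot tell us.

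None of this threatens the feasibility of the study, but the properties claimed for it should be made true or removed.

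**What to change.** - **Section 9.2 and synopsis.** Replace the single 90% by the evaluable number and power in each group, with the SD and the split assumed. State that 1590 is the number enrolled before drop-out.
- **Section 9.3.1.** Replace the overall 5% level by 5% per test. A Holm procedure over the two primary group tests is an option, not a necessity.
- **Section 9.3.3, primary endpoint.** Use GP-cluster-robust standard errors for the mean change in each group. Equivalent alternatives are a GP random effect in a model of the change score, or a GP-by-visit random effect in a model of the raw scores. A GP random intercept on raw scores is not enough: it is common to both visits, cancels in the difference, and leaves GP variation in the change unaccounted for.

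The cost is a few sentences and one change to the analysis, which can be completed in the SAP before database lock. The downside is slightly wider intervals if the ICC is positive: by √1.05 to √1.25, about 2% to 12%, over the assumed range. No extra patients are needed.
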